6.1 Risks

Potential risks to PCSO participating in MILO include: 1) There is a potential risk that confidential health information collected during the course of the study may be disclosed to others. 2) Participating PCSO may at times feel inconvenienced by the time required to complete the sessions and/or research assessments. 3) Participants may experience frustration or anxiety in learning to use the motivational interviewing communication skills. They may experience sadness or discomfort when discussing personal problems or in interacting with a family member. Discussing or experiencing the IP's psychiatric problems may be upsetting to the family. 4) There is a potential risk that participants will be subjected to stigma or undue anxiety from identification with the study. 5) The individuals with psychosis will be discussed in detail during study sessions. These individuals might find it distressing to know that their circumstances are the topic of their loved ones' research participation.

The PI and study staff will take the following steps to protect against risks:

- 1) Confidentiality will be maintained by assigning each participant a study number, and coding all data collected with that number. Identifying information and study data will be stored separately on secure BMC servers. To protect the confidentiality of the IP being discussed, his/her name will not be written down anywhere. All computer databases will be password protected, and hard copies of all data and records will be stored in locked filing cabinets. All study personnel will be certified to conduct research with human subjects and will be aware of the importance of maintaining strict confidentiality. Audio recordings of participants will be saved in digital files on a secure BMC server. Audio files will be destroyed at the conclusion of the study unless explicit consent to use audio files (e.g. for training purposes) is obtained from participants.
- 2) The assessment battery has been designed to minimize participant burden.

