7.1 Subject Inclusion Criteria

In order to be eligible to participate in this study, an individual must meet all of the following criteria:

- PCSO is 18 years or older
- PCSO is able to communicate in English
- PCSO is a primary care giver or an individual who has ≥20 hours weekly contact with an IP
- PCSO is able to provide informed consent by demonstrating that they understand the aims and structure of the study

Although the individual with psychosis will not participate in MILO, study staff will establish via the participating PCSO that the individual with psychosis is:

- Aged 15-35
- Has been diagnosed with a DSM-5 psychotic disorder by a health professional, OR has clearly observable (by the PCSO) symptoms/behaviors indicating psychosis
- Experienced onset of observed symptoms or first psychosis diagnosis occurred within past five years
- Is not optimally engaged in outpatient treatment

Identifiable information about the individual with psychosis is not kept in study records. The information gathered about the IP is based on participants' reporting and perceptions.

Subject Exclusion Criteria

An individual who meets any of the following criteria will be excluded from participation in this study:

- Current mental health crisis: if study staff determine that the potential participant is in serious emotional distress during the eligibility determination and consent process, staff will consult with the PI to determine whether the participant should be referred to psychiatric care to address their distress prior to participating in MILO

8 Study Intervention

The active intervention includes four to five 45-60 minute sessions. Sessions will be conducted individually with the clinician, or if two or more PCSO (e.g., parents) wish to participate together, they will meet at the same time with the clinician. The first two sessions will focus primarily on teaching through concept review, demonstration, and role play. In the third and fourth sessions, the clinician will learn about PCSOs' efforts to initiate a conversation about treatment with the IP using, and will provide feedback, problem-solving, and encouragement regarding the PCSO's

efforts. A fifth session may be offered upon request to provide additional coaching, consultation, and psychoeducation relevant to MILO topics. See Table 1 for details about session content.

Session	Content

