Consent	If potential participant is eligible, they are offered a time to review the study consent with study staff. Once study details have been reviewed and study staff have made sure participants have no lasting questions, then study staff send the REDCap consent link to the participants. Participants are given study staff contact information if they have any more questions before signing the document via REDCap. If participants do not have access to necessary technology to complete a remote consent, they will be invited to [name] office. All in person operations will follow BMC's COVID procedures.
Baseline Assessments	Participants are sent a REDCap survey link after consent is complete via email and asked to schedule a 15 minute phone call with study staff to complete their baseline real play assessment
Randomization	Once baseline assessments are complete, study staff randomize participant into MILO or waitlist condition.
IF Waitlist Condition	Participants randomized to waitlist condition, are emailed the date that their waitlist period ends and offered a 30 minute treatment consultation with one of the MILO trainers before the 6 week waitlist period is complete. This treatment consultation can be completed over the phone, over a BMC Zoom, or in person at [name] office. All in person visits will follow BMC's COVID procedures. At the end of the waitlist period, they are sent REDCap surveys and asked to complete another real play assessment over the phone (first done at baseline).
MILO Treatment	Participants randomized to immediate MILO, as well as those who have already finished the waitlist period, are scheduled for their first MILO training session. Sessions are offered via a secure telehealth platform, HIPAA compliant Zoom or in person if the participant does not have access to appropriate technology. All in person operations will follow BMC's COVID procedures. Sessions are 45-60 minutes and participants are offered 4-5 sessions. All sessions are conducted by trained study staff. Study staff receive weekly individual supervision from the PI.

	Study staff utilize detailed guides to ensure high fidelity to the MILO intervention. Details of the intervention are described in the table above in section 8.
Post-Intervention Assessments	Once participants have completed MILO intervention, they are emailed their post-intervention REDCap survey and asked to schedule their last real play audio recorded exercise over the phone.

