11.2 Sample Size Determination

The overall target for recruitment is 100 participants. 52 participants will be recruited for the protocol once approved by BMC (48 participants were recruited at Beth Israel Deaconess Medical Center which was the original recipient of the K23 funding support). This study is a pilot intended to test feasibility and preliminary effectiveness of the MILO intervention. Although true “pilot” studies focus an on intervention’s feasibility, rather than effects per se, the current study reflects a two-phase hybrid of priorities balancing the need to focus on feasibility while also investigating whether the intervention impacts the hypothesized treatment targets (MI skills, self-efficacy) and whether it is more effective in achieving the primary outcome (IP engagement in FEP treatment) than a control condition representing “treatment as usual” and a waiting period. The control group will be small relative to the active treatment group, thus maximizing the feasibility-focused sample. Thus the study may be somewhat underpowered to detect statistically significant effects, but has been designed to yield high quality feasibility metrics, highlight important factors for implementation, and provide a rough estimate of effect size that will inform a later, fully powered RCT.

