11.3 Statistical Methods

Feasibility will be analyzed using the following descriptive metrics: # participants screened; # Eligible; # Enrolled; # not enrolled and corresponding reasoning # Meeting DSM-5 Adjustment Disorder criteria; Percentage of Treatment sessions completed; Treatment Satisfaction; % assessments completed; Duration of assessments.

The outcomes of interest will be compared between the intervention and waitlist groups, and also within the waitlist group (comparing the pre-post intervention changes to the pre-post waitlist time changes. Prevalence of IP treatment seeking in each group will also be analyzed via odds ratios. Secondary outcomes, i.e. changes in PCSO distress and quality of life, will be

assessed via repeated measures ANOVAs examining group-by-time changes. Similarly, hypothesized mediators of effects (MI skill proficiency and self-efficacy) will be examined via repeated measures ANOVAs examining group-by-time changes. Analyses will be conducted using SPSS software.

12 Ethics/Protection of Human Subjects

This study is to be conducted according to applicable US federal regulations and institutional policies (which are based in federal regulations, guidance, and ICH Good Clinical Practice guidelines).

This protocol and any amendments will be submitted to the Boston Medical Center and Boston University Medical Campus IRB, for formal approval of the study conduct. The decision of the IRB concerning the conduct of the study will be made in writing to the investigator. A copy of the initial IRB approval letter will be provided to the sponsor before commencement of this study.

All subjects for this study will be provided a consent form describing this study and providing sufficient information for subjects to make an informed decision about their participation in this study. The consent form will be submitted with the protocol for review and approval by the IRB. The consent of a subject, using the IRB-approved consent form, must be obtained before that subject is submitted to any study procedure. Consent will be documented as required by the IRB.

13 Literature References

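### Two caregivers of one individual with psychosis may take part together, but the plan sets no family unit for allocation, counting or analysis

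*Combined protocol and SAP*

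**What the plan says.** Section 8 (Study Intervention) makes individual sessions the norm but adds that "if two or more PCSO (e.g., parents) wish to participate together, they will meet at the same time with the clinician". Section 7.1 sets eligibility caregiver by caregiver, and nothing there restricts a family to one enrolled caregiver.

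The randomization row of the table in section 9 reads: "Once baseline assessments are complete, study staff randomize participant into MILO or waitlist condition". It gives no rule for caregivers who want to attend together.

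Section 11.2 counts the target of 100 in participants and does not say how many IPs or families that represents. It wants to know "whether it is more effective in achieving the primary outcome (IP engagement in FEP treatment) than a control condition", and to obtain an approximate effect size for a later trial. It also records that "48 participants were recruited at Beth Israel Deaconess Medical Center", which leaves 52 to recruit under this version.

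Section 11.3 states: "Prevalence of IP treatment seeking in each group will also be analyzed via odds ratios". Caregiver outcomes go to repeated measures ANOVA with a group-by-time term. There is a further comparison "within the waitlist group (comparing the pre-post intervention changes to the pre-post waitlist time changes". No family term, cluster adjustment or rule for two reports on the same IP appears.

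On linkage, section 7.1 says "Identifiable information about the individual with psychosis is not kept in study records", and section 6.1 adds: "To protect the confidentiality of the IP being discussed, his/her name will not be written down anywhere". No family code is described.

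**The concern.** IP engagement belongs to the IP, not to the caregiver. Past-month service use is collected from each participant, so two enrolled parents give two records, possibly discordant, of one person's treatment. The planned analyses treat these as independent. What follows depends on the missing allocation rule.

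- **(a) Joint attenders share an arm.** Joint sessions imply this. One IP's outcome is then counted twice in that arm, and the naive standard errors are too small. Two caregivers' scale scores are also likely to be correlated.
- **(b) Each caregiver is randomised singly.** Section 9 says this if read literally. About half of pairs then fall across arms. A split IP is counted once in each arm, may be influenced by the trained caregiver, and contributes no difference. Pairs who are both waitlisted still make the within-waitlist comparison look too precise.

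The product of the comparison is an effect size for planning a larger trial. Under (a) that estimate looks more precise than it is; under (b) it is biased towards zero. The section 4.2.1 feasibility outcomes are descriptive and involve no between-arm test, but a count of participants would not show how many IPs the study covers.

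**Working it through.** **The plan's own figure.** 48 + 52 = 100, which agrees. No alpha, power, event rate or intraclass correlation (ICC) is given, so 100 cannot be derived from a power calculation.

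**Inputs.** From the documents: N = 100 and 50:50 allocation (sections 2 and 5). Section 11.2 describes a smaller control group; the calculations use 50:50. Assumed, because the documents are silent: *f*, the share of the 100 caregivers who are in pairs with one IP (10%, 20%, 40%, 60%); the within-pair ICC; a nominal two-sided 5% test; a 30% event rate under the null; and 30% v 50% engagement for the dilution example.

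**(a) Pairs share an arm.** Design effect DE = 1 + *f* × ICC. Effective N = 100/DE. True type I error of a test that assumes independence = 2 × (1 − Φ(1.96/√DE)). ICC = 1 is the ceiling, where both caregivers report the IP identically. For the scales, the relevant ICC is that of the change over time; 0.5 is illustrative.

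| *f* | 10% | 20% | 40% | 60% |
|---|---|---|---|---|
| DE, ICC 1 | 1.1 | 1.2 | 1.4 | 1.6 |
| Effective N | 91 | 83 | 71 | 62.5 |
| Type I error, formula | 6.2% | 7.4% | 9.8% | 12.1% |
| Simulated, ICC 1 | 5.8% | 7.0% | 9.5% | 11.7% |
| Simulated, ICC 0.8 | 5.2% | 6.5% | 8.6% | 10.4% |
| Scales, ICC 0.5, formula | 5.6% | 6.2% | 7.4% | 8.6% |

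The simulated rows test the log odds ratio (20,000 runs). A separate simulation with a pooled two-proportion test (40,000 runs) gave 7.6%, 10.2% and 12.5% at *f* = 20%, 40% and 60% with ICC 1, against 5.2% with no pairs.

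**(b) Caregivers randomised singly.** Given one caregiver's arm, 50 of the other 99 places are in the opposite arm, so P(pair split) = 50/99 = 0.505. The fraction of each arm made up of split pairs is *q* = 0.505 × *f*. Those IPs have the same outcome in both arms, so the expected risk difference is (1 − *q*) × the true one. If a split IP has the MILO rate, the waitlist arm is expected to show 30% + 20% × *q*. The odds ratio is then (1 − that rate)/(that rate), because the MILO odds are 1.

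| *f* | 0 | 10% | 20% | 40% | 60% |
|---|---|---|---|---|---|
| Split pairs | – | 2.5 of 5 | 5.1 of 10 | 10.1 of 20 | 15.2 of 30 |
| Dilution (*q*) | – | 5% | 10% | 20% | 30% |
| 20-point difference becomes (simulated) | 20 | 19.1 | 18.0 | 16.0 | 14.0 |
| Odds ratio becomes (formula) | 2.33 | 2.22 | 2.12 | 1.94 | 1.77 |
| Power (simulated) | 54% | 51% | 46% | 38% | 30% |
| Type I error (simulated, log odds ratio) | – | 4.7% | 4.5% | 4.5% | 4.4% |

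Type I error is not inflated here; the pooled test gave 5.0% to 5.3%. The dilution is the same within simulation error if only half the effect reaches a split IP, because its single outcome still counts in both arms.

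**Within-waitlist comparison under (b).** A waitlisted caregiver's partner is also waitlisted with probability 49/99. So DE = 1 + *f* × 49/99 at ICC 1 (a ceiling) = 1.05, 1.10, 1.20, 1.30. The square roots are 1.02, 1.05, 1.09, 1.14, so the true standard error is up to about 2%, 5%, 9% and 14% larger than stated.

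**The case against.** The strongest reply concerns weight. Joint attendance is an option on request, the documents give no share of pairs, and nothing supports 40% or 60%. At 10% to 20% in pairs, reading (a) gives a simulated 5.2% to 7.0% for IP engagement at ICC 0.8 to 1. That stands: if few pairs enrol, the effect is small.

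Reading (b) fits section 8 poorly. Caregivers split across arms would start about six weeks apart and could not attend the same course together unless the allocation were overridden. That makes (a) the likelier practice, but no section says so, and section 9 taken literally gives (b).

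This is also a pilot with descriptive primary outcomes and an admission that it may be underpowered, so no declared decision rule turns on an exact 5%. That lowers the stakes. It does not cover double counting or dilution, which distort the effect size or its precision. Under (a) the point estimate itself is not shown to be biased.

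Shared IPs could probably be traced, since caregiver contact details and clinician notes are kept. This is fair, and it is what makes back-coding feasible. The link would still be missing from the analysis data set unless someone adds it.

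Finally, the section 5 figure and the Appendix schedule are not in the text available here, so a rule there cannot be excluded. That two joint attenders concern one IP is inferred from the example of parents, which is the natural reading.

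**Conclusion.** The concern holds. The sections that should define the unit (7.1, 8, 9, 11.2 and 11.3) allow several caregivers per IP and then analyse as if each were independent. Followed as written, the plan either counts an IP twice in one arm or counts it in both arms.

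The first case gives type I error of up to about 6% to 12%. The second gives no inflation, but dilution of about 5% to 30%. Both ranges rest on an assumed 10% to 60% of caregivers in pairs and on ICC 1 for the first. The true share is unknown, and at the low end the consequence is modest. It should be fixed because it affects the comparison that section 11.2 itself treats as primary, and because the remedy is cheap while 52 participants remain to be recruited.

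**What to change.** For the remaining participants, make one allocation per IP or family, so that all caregivers of one IP receive the same arm, and record a de-identified family code in REDCap. A code of this kind respects the confidentiality rules.

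In section 11.3:
- Analyse IP engagement once per IP. Fix the informant by a rule that also works retrospectively, for example the caregiver randomised first (lower study number if tied). That caregiver's arm is the IP's arm.
- For caregiver outcomes, including the within-waitlist comparison, use cluster-robust standard errors or a family random effect. With few pairs a random effect may be poorly estimated.
- Report the number of distinct IPs and of families with more than one caregiver.

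For families already enrolled, add the code and apply the same analysis. Where a family was split across arms, report how many and add a sensitivity analysis without them, because analysis cannot remove contamination.

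The cost is a small procedural change, one coded field with back-coding, and SAP wording. Intervals widen slightly. At 80% power and an assumed ICC of 0.3 to 0.5, the detectable standardised difference on caregiver scales moves from 0.56 to 0.58–0.59 with 20% in pairs, or 0.59–0.61 with 40%. Families already split cannot be repaired. If the intent is that only one caregiver per IP is enrolled, one sentence in section 7.1 would settle the point.

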The PI ([name]) has developed a brief 4-5 session training course for caregivers called "motivational interviewing for loved ones" (MILO). Each training session lasts 45-60 minutes and consists of teaching the participant an MI based communication skill, reviewing previously discussed skills, or offering referral information for treatment for their IP. The training can be done in-person or virtually. In a feasibility focused pilot, the intervention was found to be highly valued by participants, with 94% of consented participants completing at least three sessions. This application represents the continuation of a pilot efficacy trial that was initiated at Beth Israel Deaconess Medical Center and which the PI would like to continue at Boston Medical Center.

This study will be conducted in compliance with the protocol, applicable regulatory requirements, and BMC/BU Medical Campus Human Research Protection policies and procedures.

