The study is designed to minimize participant burden. Concerns about the ethics of randomization are allayed by the fact MILO is untested (effectiveness is not proven), and that the control condition represents treatment as usual. Thus the risk benefit ratio, even for those assigned to “treatment as usual/waitlist”, is favorable given that typically no particular assistance is offered in the community for parents/significant others attempting to connect their loved one with care. Phase 1 of the study was completed at its initial site at Beth Israel Deaconess Medical Center. Phase 2 was also started at the previous sight and will be completed at Boston Medical Center.

We will be collecting data through REDCap surveys administered via email link to the participants. Those assigned to the MILO treatment condition will be assessed at 4 time points (study entry, post intervention, 8 week follow up, 12 week follow up). Those in the waitlist condition will be assessed at 5 time points (study entry, end of waitlist, post intervention, 8 week follow up, 12 week follow up). Please see the following measures:

- Participants Contact Information
- Demographics questionnaire
- SCID-5 Adjustment disorder module
- Absolute Worth and Autonomy Scale
- Perceived Stress Scale
- Conflict Behavior Questionnaire
- SCORE-15 Index of Family Functioning
- Parenting Self-Agency
- Family Questionnaire
- Motivational Interviewing Skills Questions
- Mental Health Service Use History & Past month Service Use History Forms
- Modified Client Satisfaction Questionnaire
- Change Questionnaire

- 10-minute audio-recorded standardized patient role play (at study entry and post-intervention and waitlist time points only; role-plays will be scored using the Motivational Interviewing for Loved Ones Skills Assessment.

6 Potential Risks and Benefits

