6.2 Potential Benefits

If it is effective, the intervention has tremendous upside to both participants and their loved ones with psychosis. The goals of the intervention are to shorten DUP, increase service utilization by the IP, and reduce caregiver distress. These parents and other loved ones are often desperate to seek help on behalf of the IP. Learning MI skills may benefit participants by reducing their stress, helping them to feel more confident in their caregiving role, and giving them information about how they can better facilitate the IP's connection or adherence to treatment.

Those randomized to the waitlist will be offered a 30-minute consultation during which the PCSO is provided with information about treatment options (e.g., community mental health and FEP coordinated specialty care programs) and contact information for an active NAMI chapter in his/her area. This will be done in person or by telephone. This consultation represents the minimum standard of care for caregivers of individuals with recent-onset psychosis being treated at BMC. Additionally, waitlist participants will have the opportunity to receive MILO training after a six-week wait.

Concerns about the ethics of randomization are allayed by the fact MILO is untested (effectiveness is not proven), and that waitlisted participants will also be offered the MILO intervention after a short waiting period.

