8 Week Follow Up	Participants are emailed a REDCap survey 8 weeks after their last MILO session.
12 Week Follow Up	Participants are emailed their last REDCap survey 12 weeks after their last MILO session.

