11.1 Study Hypotheses

1. The MILO intervention will be feasible and acceptable for participants.
2. The MILO intervention will impact outcomes of interest (e.g., proficiency using MILO skills, confidence, stress, caregiving attitudes, and caregiver-reported IP treatment engagement).
3. Participants attending MILO sessions will show more improvement with regard to outcomes of interest within the first six weeks of study participation relative to those on the waitlist.
4. After attending MILO sessions, waitlisted participants will “catch up” to those randomized to receive the intervention immediately with regard to changes on outcomes of interest.
5. Gains in MI proficiency as demonstrated via scored audio recordings will mediate the impact of the intervention on other outcomes such as reduced conflict and stress and increased confidence and caregiver-reported IP treatment engagement.

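### After MILO, outcome assessment is triggered by completing treatment, while the waitlist is surveyed by calendar, so non-completers may go unassessed in one arm of the randomised contrast

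*Combined protocol and SAP*

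**What the plan says.** Section 5 (Study Design) plans assessment by assignment: "Those assigned to the MILO treatment condition will be assessed at 4 time points". It gives no dates and no rule for people who leave the sessions early.

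Section 9 (Study Procedures) gives the operating rules:

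- Post-intervention survey and role play: "Once participants have completed MILO intervention, they are emailed their post-intervention REDCap survey". What counts as completion is not defined, although four sessions are planned and a fifth is optional.
- Eight-week survey: "Participants are emailed a REDCap survey 8 weeks after their last MILO session".
- Twelve-week survey: "Participants are emailed their last REDCap survey 12 weeks after their last MILO session".
- End-of-waitlist assessment: "At the end of the waitlist period, they are sent REDCap surveys and asked to complete another real play assessment". This follows the calendar. Section 6.2 gives the length: "waitlist participants will have the opportunity to receive MILO training after a six-week wait". Section 8 lets waitlisted caregivers decline the consultation, and nothing makes their survey depend on attending it.

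Hypothesis 3 in Section 11.1 is worded by attendance: "Participants attending MILO sessions will show more improvement with regard to outcomes of interest within the first six weeks of study participation", relative to the waitlist. Section 11.3 plans odds ratios for treatment seeking by the individual with psychosis (IP) and repeated measures ANOVAs for the caregiver outcomes. It names no analysis set and no method for missing data.

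**The concern.** The randomised contrast sets the MILO arm after treatment against the waitlist arm at the end of its wait. If staff follow Section 9 literally, a record enters the MILO side only when the caregiver finishes the course, whereas the waitlist side is approached in full. Randomisation balances the arms as assigned; it does not balance finishers in one arm against everyone in the other.

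Caregivers who stop may be the more stressed, or those whose IP is hardest to engage. If so, their absence flatters MILO on both distress and engagement.

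The analysis plan does not repair this. No intention-to-treat set is named, and repeated measures ANOVA in its usual form drops anyone missing a time point. The role play is also the source of the proposed mediator in Hypothesis 5, so that analysis inherits the same selection. Section 11.2 says the study should supply a rough effect size for a later full trial, so a selection effect here would be carried into that trial's planning. Outcomes never collected cannot be recovered at analysis.

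**Working it through.** The plan states no figure on this point, so there is none to reproduce. The check has two parts.

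**1. Who is reached by each trigger in Section 9**

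| Assessment | Trigger | Completes MILO | Stops after at least one session | Never starts |
|---|---|---|---|---|
| Post-intervention survey and role play | Completion | Sent | No trigger | No trigger |
| 8- and 12-week surveys | Last session | Sent | Sent | No date to count from |

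The end-of-waitlist assessment is sent to every waitlisted caregiver at six weeks. After the wait, both arms fall under the rules in the table. The difference between arms is therefore confined to the post-MILO versus end-of-waitlist contrast. A waitlisted caregiver who never takes up MILO sits in the last column and gets no further survey.

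**2. How much it could matter, assuming no true effect**

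Inputs:

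- d, the share of the MILO arm not assessed. The only anchor is the feasibility pilot in Section 3.1, "with 94% of consented participants completing at least three sessions", which gives 1 − 0.94 = 0.06. That counts three sessions, not four, so non-completion may be higher. Values of 10% to 30% are assumptions.
- g, the gap in SD between assessed and unassessed caregivers, the same in either arm. Assumed to be 0.5.
- p, the overall engagement rate in both arms, assumed to be 0.30; q, the rate among the unassessed, assumed to be 0.10 (worse) or 0.50 (better).
- The waitlist arm is taken as fully observed.

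Formulas:

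- Continuous outcome: bias = d × g.
- Binary outcome: assessed MILO rate = (p − d × q)/(1 − d), then its odds ratio against p.
- False-positive rate: two-sided 5% normal test, 50 waitlisted caregivers against n₁ = 50(1 − d) in MILO, SE = √(1/50 + s²/n₁), with s² = 1 − d(1 − d)g².

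Worked at d = 0.20:

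- Bias = 0.20 × 0.5 = 0.10 SD.
- s² = 1 − 0.16 × 0.25 = 0.96; SE = √(0.020 + 0.96/40) = 0.210; shift = 0.10/0.210 = 0.48 standard errors; false-positive rate 7.6%.
- With q = 0.10: (0.30 − 0.02)/0.80 = 0.35; odds ratio (0.35/0.65)/(0.30/0.70) = 1.26.

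| d | Bias, 0.5 SD gap | False-positive rate | Odds ratio, q = 0.10 | Odds ratio, q = 0.50 |
|---|---|---|---|---|
| 6% | 0.03 SD | 5.3% | 1.06 | 0.94 |
| 10% | 0.05 SD | 5.7% | 1.11 | 0.90 |
| 20% | 0.10 SD | 7.6% | 1.26 | 0.78 |
| 30% | 0.15 SD | 10.6% | 1.47 | 0.64 |

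If the unassessed do the same as the rest (q = 0.30, or g = 0), the bias is nil. If they do 0.5 SD better, the continuous bias has the same size with the opposite sign. The 50 per arm comes from the equal split of 100 in the Protocol Summary. Section 11.2 describes a smaller control group, which would change the false-positive rates but not the biases or odds ratios.

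**The case against.** A reader might infer more than the text supports, and the case on the other side is good on several counts.

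- **That non-completers are excluded from assessment.** Section 9 does not say the survey goes only to completers, and completion could be read as having finished attending. Section 5 plans four assessments for everyone assigned to MILO. This stands: the two sections conflict, and nobody is excluded outright. But nothing tells staff how or when to survey someone who stops, so Section 5 alone does not close the gap.
- **That early stoppers also lose the 8- and 12-week surveys.** They do not. One attended session supplies a last session to count from; only never-starters lack it.
- **That the whole waitlist arm yields outcomes.** Its members are sent surveys, and return is not guaranteed. The calculation above is idealised in this respect.
- **That later results also have different rules by arm.** They do not, because both arms then face the same triggers. Those results are limited to people who took up MILO, which is a different weakness.
- **That the bias must favour MILO.** No data in the documents settle this. A caregiver may stop because the IP has entered care, and the bias would then run against MILO.

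It is also fair to say that feasibility is the primary outcome in Section 4.2.1, with assessment completion among its metrics, and that the pilot suggests few early stoppers. Against that, Sections 3.2, 5 and 11.2 call IP engagement primary, and an assessment-completion rate has an unclear denominator if some surveys are never sent.

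Section 9 refers to an appendix schedule of events that is not in the text available here. If it contains a rule for non-completers, Section 9 should agree with it.

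**Conclusion.** The point holds in limited form. Section 9 makes outcome collection depend on treatment completion in one arm of the post-MILO versus end-of-waitlist contrast, conflicts with the by-assignment plan in Section 5, and is not repaired by Section 11.3. The comparison may be biased, probably but not certainly towards MILO; the direction is a judgement about why caregivers stop.

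The size cannot be known from the documents. At the pilot-based 6% it is small. At 20% to 30% it would be material for an effect estimate meant to inform a later trial. Every figure beyond the 6% rests on assumed non-completion, an assumed gap and a fully returned waitlist survey, so none should be read as the expected bias.

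**What to change.** Reconcile Section 9 with Section 5 and amend as follows:

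- Send the post-intervention survey and role play to everyone assigned to MILO on completion or on stopping. For those who stop or never start, send them no later than a default date fixed from randomisation, for example the same six weeks as the waitlist survey. Define completion.
- Date the 8- and 12-week surveys from the last session or, if there was none, from that default date. For waitlisted caregivers who do not take up MILO, date them from the end of the wait.
- State that stopping sessions does not stop surveys unless consent is withdrawn.
- In Section 11.3, state that the analysis is by assigned arm with these records included, and name a missing-data method for ordinary non-response.
- Apply this to participants still to be assessed. For earlier participants, including those among the 48 recruited at the first site, report by arm any surveys that were not sent.

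The cost is wording and REDCap links, plus the role-play calls to non-completers; no new instruments are needed. The price is a lower reported return rate and possibly a smaller observed effect. The change removes the bias due to the trigger but not that due to unreturned surveys. Completers would still be assessed at varying times against a fixed six weeks, which is a separate matter of timing.
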